| 2 | 27-Aug-2020 | 
There are a very limited number of patients who are exposed to the new dosage Dupilumab 300 mg q4w. As a consequence, the full analysis set and modified analysis set is highly overlapped. Safety subgroup analyses will be performed on the full analysis set which represents the overall safety evaluation of the study population.
 | "The planned subgroup analyses for key safety endpoints will be performed for each of the full and modified analysis sets of safety population" will be changed to "The planned subgroup analyses for key safety endpoints will be performed for the full analysis set of safety population" |
| 2 | 27-Aug-2020 | Antigen-specific IgE will be assessed along with the total IgE | Add analyses for antigen-specific IgE |

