2 STATISTICAL AND ANALYTICAL PROCEDURES

Generalities

Generally, for each analysis population (Safety, Efficacy, Pharmacokinetics, and Anti-drug antibody) that is defined in [Section 2.3](#), the planned analyses will be conducted in the following two analysis sets:

- The full analysis set: all data observed in the study. The analyses performed on the full analysis set are to evaluate the long-term safety, efficacy, PK and etc. of all the dose regimens that are investigated in the LTS14424 study, that is, dupilumab 100 mg q2w, 300 mg q4w and 200 mg q2w.
- The modified analysis set: 1) For patients never exposed to 300 mg q4w: all observed data will be included 2) For patients that switch from 100 mg q2w to 300mg q4w in LTS14424: data will be included up to the date of first dose of 300 mg q4w with censoring data observed on or after this date 3) For patients that initiate the study on 300 mg q4w (i.e. receive 300 mg q4w at Day 0) no data will be included in this analysis set. The analyses performed on the modified analysis set are to focus on the long-term safety, efficacy, PK and etc. of the same regimens as the parent study, that is, dupilumab 100 mg q2w and 200 mg q2w.

Observation period

The observation period will be divided into 4 epochs which are defined in [Table 3](#) according to the two analysis sets.

The treatment-emergent adverse event period will include both treatment and residual treatment epochs that are defined in [Table 3](#). The post-treatment adverse event period will be the post-treatment epoch.

The pre-treatment adverse event period will be from the start of AE reporting in LTS14424 up to the first dose of IMP in LTS14424. For all the periods aforementioned, both date and time shall be used in the determination of the periods, as long as they will be available.

Table 3 - Study epoch definition by analysis set

| Analysis Set | Epoch | Applicable Patients | Epoch Start | Epoch End |
|-------------------|--------------------|---------------------------------------------------|-----------------------------------|-----------------------------------------------|
| Full analysis set | Screening | All | – | The day before the date of first IMP |
| | Treatment | Patients with last IMP on 100mg/200mg q2w regimen | Date of the first IMP in LTS14424 | Date of last IMP +14 days |
| | | Patients with last IMP on 300 mg q4w regimen | Date of the first IMP in LTS14424 | Date of last IMP +28 days |

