| | Residual treatment | Patients with last IMP on 100mg/200mg q2w regimen | Date of last IMP +15 days | Date of last IMP +14 days +12 weeks (84 days) |

| Analysis Set | Epoch | Applicable Patients | Epoch Start | Epoch End |
|------------------------------------------------------------------------------------------------------------------------------|--------------------|-------------------------------------------------------------|----------------------------------------------|-----------------------------------------------|
| | | Patients with last IMP on 300 mg q4w regimen | Date of last IMP +29 days | Date of last IMP +28 days +12 weeks (84 days) |
| | Post-treatment | All | Residual treatment Epoch End date +1 day | Open ended |
| Modified analysis set (not applicable to patients who initiate the treatment on 300 mg q4w regimen since Week 0 of LTS14424) | Screening | All | -- | The day before the date of first IMP |
| | Treatment | Patients on 100 mg/200 mg q2w regimen only | Date of the first IMP in LTS14424 | Date of last IMP +14 days |
| | | Patients who switched regimen from 100 mg q2w to 300 mg q4w | Date of the first IMP in LTS14424 | The date before the first dose of 300 mg q4w |
| | Residual treatment | Patients on 100 mg/200 mg q2w regimen only | Date of last IMP +15 days | Date of last IMP +14 days +12 weeks (84 days) |
| | | Patients who switched regimen from 100 mg q2w to 300 mg q4w | N/A | N/A |
| | Post-treatment | Patients on 100 mg/200 mg q2w regimen only | Residual treatment Epoch End date + 1 day | Open ended |
| | | Patients ever switch regimen from 100 mg q2w to 300 mg q4w | N/A | N/A |

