2.1.3.1 Severe Exacerbation Events

A severe exacerbation event during the study is defined as a deterioration of asthma requiring:

- Use of SCS for ≥ 3 days; or,
- Hospitalization or emergency room visit because of asthma, requiring SCS.

The severe exacerbation events are collected on eCRF page “Severe Asthma Exacerbation”.

Both number and annualized rate of severe exacerbation events will be analyzed. For each analysis set, the total number of events is defined as the number of events that have onset between the start date and the end date of the Treatment Epoch ([Table 3](#)). The standardized on-treatment duration (in years) will be calculated by (End date of the Treatment Epoch - Start date of the Treatment Epoch +1)/365.25.

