2.4.3.1 Extent of investigational medicinal product exposure

The extent of IMP exposure will be assessed by the duration of IMP exposure in LTS14424 study.

For each analysis set, duration of IMP exposure is defined as End date of the Treatment Epoch – Start date of the Treatment Epoch +1 as defined in [Table 3](#), regardless of unplanned intermittent discontinuations (see [Section 2.5.2](#) for calculation in case of missing or incomplete data).

Duration of IMP exposure will be summarized descriptively as a quantitative variable (number, mean, SD, median, minimum, and maximum). In addition, duration of treatment exposure will also be summarized categorically by numbers and percentages for each of the following categories and cumulatively according to these categories:

- >0 and \leq 2 weeks
- > 2 and \leq 4 weeks
- > 4 and \leq 8 weeks
- > 8 and \leq 12 weeks
- > 12 and \leq 16 weeks
- ...
- ...
- > 48 and \leq 52 weeks
- > 52 weeks

Additionally, the cumulative duration of treatment exposure, will be provided in patient years by treatment category and overall.

Number and percentage of patients will be summarized by total number of injections they received during the LTS14424 study.

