2.4.5.1 Analyses of adverse events

Generalities

The primary endpoint of this study is the number (n) and percentage (%) of patients experiencing any treatment-emergent adverse events (TEAE). Pre-treatment and post-treatment adverse events will be described separately if applicable.

If an adverse event date/time of onset (occurrence, worsening, or becoming serious) is incomplete, an imputation algorithm will be used to classify the adverse event as pre-treatment, treatment-emergent, or post-treatment. The algorithm for imputing date/time of onset will be conservative and will classify an adverse event as treatment-emergent, unless there is definitive information to

determine it is pre-treatment or post-treatment. Details on classification of adverse events with missing or partial onset dates are provided in [Section 2.5.2](#).

Adverse event incidence tables will be presented by system organ class (SOC), high level group term (HLGT), high level term (HLT) and preferred term (PT) sorted in alphabetical order, to summarize the number (n) and percentage (%) of patients experiencing at least one AE in each analysis set of safety population by the treatment category. Multiple occurrences of the same event in the same patient will be counted only once in the tables within a treatment category. The denominator for computation of percentages is number of patients in each analysis set of safety population by the treatment category. In all AE incidence tables, the total patient years (in the unit of 100 patient-years) of each analysis set of safety population by the treatment category will be presented in the corresponding column headers.

The number of events per 100 patient-years (adjusted for the total duration of exposure) of each analysis set of safety population by the treatment category will be presented for each AESI during the corresponding treatment-emergent period.

Sorting within tables ensures the same presentation for the set of all adverse events within the observation period (pre-treatment, treatment-emergent, and post-treatment). For that purpose, the table of all TEAEs presented by SOC and PT sorted by the internationally agreed SOC order and decreasing frequency of PTs within SOCs will define the presentation order for all other tables unless otherwise specified. Sorting will be based on the results for the overall patients across treatment categories, unless otherwise specified.

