 - Cumulative incidence (K-M estimates) up to specified time points (Week 4, Week 12, Week 24, Week 36, Week 52, Week 64).

Notes for the last bullet: when TEAE start date or worsening date is partially available, the maximum of the earliest possible TEAE start date and the treatment start date will be used. When TEAE start date or worsening date is completely missing, the treatment start date will be used.

- Number of treatment-emergent AESIs and other selected AE groupings per 100 patient-years (total number of events adjusted for the total duration of exposure) will be presented by decreasing incidence of PT within each AESI and other selected AE groupings category.
- The time-to-first AESI event analyzed using Kaplan-Meier (K-M) methods and displayed as K-M plots (cumulative incidence (%)) versus time based on K-M estimates) will be provided to depict the course of onset over time.
- A listing will be provided for AESIs.

Analysis of pre-treatment and post-treatment adverse events

- All pre-treatment AEs by primary SOC and PT, showing the number (%) of patients (including total patient years in column headers) with at least 1 pre-treatment AE, will be presented by the internationally agreed SOC order and by decreasing incidence of PTs within each SOC.
- All pre-treatment SAEs by primary SOC and PT, showing the number (%) of patients (including total patient years in column headers) with at least 1 pre-treatment SAE, will be presented by the internationally agreed SOC order and by decreasing incidence of PTs within each SOC.

- All post-treatment AEs by primary SOC and PT, showing the number (%) of patients (including total patient years in column headers) with at least 1 post-treatment AE, will be presented by the internationally agreed SOC order and by decreasing incidence of PTs within each SOC.
- All post-treatment SAEs by primary SOC and PT, showing the number (%) of patients (including total patient years in column headers) with at least 1 post-treatment SAE, will be presented by the internationally agreed SOC order and by decreasing incidence of PTs within each SOC.

Analysis of adverse events

- All pre-treatment, treatment-emergent, or post-treatment AEs by primary SOC and PT, showing the number (%) of patients (including total patient years in column headers) with at least 1 AE, will be presented by the internationally agreed SOC order and by decreasing incidence of PTs within each SOC.

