3 INTERIM ANALYSIS

This is 1-year treatment safety study. At the time of the initial dupilumab marketing authorization application for the treatment of Asthma in pediatric of 6 to <12 years old, an interim database lock will be performed. In addition, interim analyses/reports may be prepared to support regulatory submissions or other purposes. No alpha adjustment is needed for the final CSR.

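### Main-study AESI and selected-AE rates per 100 patient-years count events for 84 days beyond the exposure time they appear to be divided by, which puts them about 23% above a matched rate for completers

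*SAP*

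**What the plan says.** **The rate.** SAP 2.4.5.1 (Generalities) plans "The number of events per 100 patient-years (adjusted for the total duration of exposure) of each analysis set of safety population", by treatment category, for each AESI in the treatment-emergent period of that analysis set. The AESI part of the same section repeats it more widely: "Number of treatment-emergent AESIs and other selected AE groupings per 100 patient-years (total number of events adjusted for the total duration of exposure". Protocol 11.4.3.1.2 describes the AESI rate in the same terms.

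**The numerator window.** SAP section 2 states: "The treatment-emergent adverse event period will include both treatment and residual treatment epochs". In Table 3 the residual epoch of a patient whose last dose was on a q2w regimen ends at "Date of last IMP +14 days +12 weeks (84 days". For 300 mg q4w the first term is 28 days instead of 14.

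**The denominator.** Neither place in 2.4.5.1 gives a formula or a cross-reference. In SAP 2.4.3.1, "duration of IMP exposure is defined as End date of the Treatment Epoch" minus its start date plus one day, and that section totals this exposure in patient-years. Table 3 ends the Treatment Epoch 14 or 28 days after the last dose. Protocol 11.4.1.1 also stops at one dose interval. No patient-year quantity that covers the residual epoch is defined anywhere. The patient-year totals promised in the AE table column headers are not tied to either period.

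**A matched rate elsewhere in the SAP.** For severe exacerbations, SAP 2.1.3.1 counts the "number of events that have onset between the start date and the end date of the Treatment Epoch" and divides by the length of that same epoch.

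**The concern.** An event rate is interpretable when the events and the person-time cover the same period. Here, if exposure means what the SAP defines it to mean, events in the 12-week residual epoch enter the numerator while the time in which they arose does not enter the denominator.

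These are the planned person-time rates for AESIs in a study whose primary objective is long-term safety. Their level would depend on a mismatch that the rate's definition does not disclose and whose size varies with retention, follow-up and cut-off. SAP section 3 says that "an interim database lock will be performed" at the time of the initial paediatric asthma application. At that point many patients may not have reached the residual epoch, so the interim and final rates could differ with no change in risk. A reader setting the rates beside those of another study would also need to know which time base was used.

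**Working it through.** **Inputs**

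- Treatment Epoch end: last dose +14 days (q2w) or +28 days (q4w). Residual epoch: a further 84 days (SAP Table 3).
- Last planned q2w dose: Week 50, Day 351 (Protocol 6.2.1). Last planned q4w dose: 28 days before the Week 52 visit, so Week 48, Day 337 (Protocol 10.1.2.10).
- Expected enrolment: 354 (SAP 1.3).

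**Reproducing the plan's own figures.** 14 + 84 = 98 days = 14 weeks, and 28 + 84 = 112 days = 16 weeks. Both agree with the treatment-emergent period in Protocol 11.4.3.1.

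**One completer with full follow-up**

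- q2w: exposure (351 − 1) + 14 + 1 = 365 days; treatment-emergent time (351 − 1) + 98 + 1 = 449 days.
- q4w: exposure (337 − 1) + 28 + 1 = 365 days; treatment-emergent time (337 − 1) + 112 + 1 = 449 days.

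Days 365 and 449 are also the SAP target days for the end-of-treatment and end-of-study visits (Table 5).

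The two rates share a numerator, so planned rate / matched rate = treatment-emergent time / exposure time = 449/365 = 1.230, whenever the events occur.

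**If all 354 complete.** Exposure: 354 × 365/365.25 = 353.8 patient-years. Treatment-emergent time: 354 × 449/365.25 = 435.2 patient-years. The difference is 81.4 patient-years. As an illustration, 30 events would give 8.48 per 100 patient-years on exposure and 6.89 on treatment-emergent time.

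**Sensitivity of the ratio (all shares are assumptions)**

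| Scenario | Ratio |
|---|---|
| 5%, 10%, 20% stop with exposure to Week 24 (169 exposure days, 253 treatment-emergent days) | 1.236, 1.243, 1.258 |
| 5%, 10%, 20% of completers have no residual follow-up | 1.219, 1.207, 1.184 |
| Interim lock: 30% finished, the rest at 273 days on treatment | 1.084 |
| Interim lock: 50% finished, the rest at 182 days | 1.154 |
| Interim lock: 80% finished, the rest at 182 days | 1.205 |
| Modified set: 5%, 10%, 20% switch to 300 mg q4w at 182 days | 1.224, 1.218, 1.205 |

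For example, the first entry is (0.95 × 449 + 0.05 × 253)/(0.95 × 365 + 0.05 × 169) = 439.2/355.2 = 1.236. In the modified set, patients censored at the switch have no residual epoch, so their own ratio is 1.00.

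**Against a purely on-treatment rate.** Let r be the event rate in the residual epoch relative to that on treatment. Then planned rate / on-treatment rate = 1 + r × 84/365. This is 1.00 at r = 0, 1.115 at r = 0.5 and 1.23 at r = 1.

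**The case against.** The denominator is inferred. Nothing in SAP 2.4.5.1 links its exposure term to the definition in 2.4.3.1, and the reference to the corresponding treatment-emergent period could be meant to set the time base as well as the numerator. On that view the SAP has an undefined term, not a mismatched rate. The same natural reading could also be applied to the column headers, which would then show readers the denominator.

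Severe exacerbation is an efficacy endpoint defined over the treatment period, so its matched window does not prove that the safety rates were meant to follow it. Placebo-Dupilumab and Dupilumab-Dupilumab patients follow the same Table 3 rules, so with similar retention the factor largely cancels between those columns. The direction is conservative: the plan raises AESI rates and does not hide a signal. The rates are descriptive, and the n (%) tables, listings and Kaplan-Meier plots cover the same event types. Each remedy has a cost, and the documents do not say which convention the parent study used.

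Much of this stands as a limit on importance. The 23% is conditional on one reading and one comparator, and comparability with other studies cannot be judged from these documents. It does not remove the point. The alternative reading needs person-time over the treatment-emergent period, and neither document defines any. A programmer who follows the written definitions would produce the mismatched rate.

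**Conclusion.** The concern holds. On the natural reading, the main-study rates count events to last dose +98 or +112 days and divide by exposure to last dose +14 or +28 days. For patients who complete treatment and follow-up, the result is 23% above a rate with matched periods. In the assumed scenarios above it ranges from 8% above (the early interim lock) to 26% above (20% stopping early). Compared with an on-treatment rate, the excess is between 0% and 23% for r between 0 and 1.

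Confidence is high that the two periods differ on this reading. It is medium on the overall size, which depends on discontinuation, follow-up and cut-off. The primary endpoint (n and % with any TEAE) and the Kaplan-Meier cumulative incidences are not affected. The contrast between full and modified sets is probably little affected, because SAP 1.6 reports: "There are a very limited number of patients who are exposed to the new dosage Dupilumab 300 mg q4w".

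**What to change.** State the person-time in SAP 2.4.5.1 and match it to the numerator, in one of two ways:

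- **(a) Treatment-emergent person-time.** Divide by time from first IMP to the earliest of last IMP +98/112 days, last contact and data cut-off; in the modified set, also stop at the day before the first 300 mg q4w dose.
- **(b) On-treatment events.** Keep IMP exposure as the denominator and count only events with onset in the Treatment Epoch, as SAP 2.1.3.1 does for exacerbations.

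Say also which patient-years the column headers show.

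Under (a) the reported rates fall, and time without dosing is added. The rate for administration-related groupings such as injection site reactions becomes (365 + 84r)/449 of the on-treatment rate, which is 0.81 if none occur in the residual epoch. Under (b) residual-period events leave the rate but stay in the n (%) tables. Using (b) for administration-related groupings and (a) for the rest would also be consistent if stated in advance and labelled.

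The cost is one sentence and one derived variable, with no new data.

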2.4.5.2 Deaths

The following summaries of deaths will be generated for the safety population, unless otherwise specified.

- Number (%) of patients who died by study period (on-study, on-treatment, poststudy)
- Deaths in non-enrolled patients or enrolled but not treated patients
- TEAE leading to death (death as an outcome on the AE CRF page as reported by the Investigator) by primary SOC, HLT, and PT showing number (%) of patients (including total patient years in column headers) sorted by internationally agreed SOC order. The other levels (HLT, PT) will be presented in alphabetical order.
- TEAE leading to death (death as an outcome on the AE CRF page as reported by the Investigator) by primary SOC and PT showing number (%) of patients (including total patient years in column headers) sorted by internationally agreed SOC order, and by alphabetical order of PT within each SOC.
- All pre-treatment and post-treatment AE leading to death by primary SOC and PT, showing the number (%) of patients (including total patient years in column headers), sorted by the internationally agreed SOC order and by decreasing incidence of PTs within each SOC.

- A listing of deaths will be provided.

2.4.5.3 Analyses of laboratory variables

The baseline value of all laboratory variables is the original baseline from the parent study. The pre-dose measurement at Week 0 of LTS14424 will be separately presented in the summaries or plots over time.

The summary statistics (including number, mean, median, standard deviation, Q1, Q3, minimum and maximum) of all laboratory variables (central laboratory values and changes from baseline) will be calculated for each visit or study assessment (baseline, each post-baseline time point, and endpoint) for each analysis set ([Section 2](#)) of safety population by the treatment category. For each continuous parameters listed in [Section 2.1.4.3](#), mean change from baseline with corresponding standard error at each visit will be plotted for each analysis set of safety population by the treatment category . This section will be organized by biological function as in [Section 2.1.4.3](#).

For all laboratory variables, the summary statistics over visits for either measurements or mean change from baseline, and the plot of mean change from baseline over visits should use the centralized data only, and should include the measurements obtained at either scheduled or unscheduled visits.

The incidence of PCSAs (list provided in [Appendix A](#)) at any time during the treatment-emergent adverse event period as defined in [Section 2](#) will be summarized by biological function, and by the treatment category for each analysis set of safety population, regardless of the baseline level and/or according to the following status at baseline of parent study and at Week 0 of LTS14424 study, respectively:

- Normal/missing.
- Abnormal according to PCSA criterion or criteria.

For parameters for which no PCSA criterion is defined, similar table(s) using the normal range will be provided.

For PCSA analyses, the laboratory measurements obtained at either scheduled or unscheduled visits should be used; and, both the centralized and local test results should be used, as long as their available dates/time is different from each other's. Centralized data will be used preferentially to the local measures in the PCSA analyses when measurements are performed on the same date and at the same time for a given laboratory test.

A listing of patients with at least 1 PCSA during the treatment-emergent adverse event period will be provided and will display the whole profile over time of all parameters of the corresponding biological function. In this listing, baseline, endpoint value and individual values will be flagged when lower or higher than the lower or upper laboratory limits and/or when reaching the absolute limit of abnormality criteria.

Drug-induced liver injury

Additional analysis of liver-related adverse events will be performed if necessary.

